6.3.12.4. Abdominal Ultrasound

An abdominal ultrasound for determination of the AFI will be performed at Screening for confirmation that subject does not have evidence of polyhydramnios or oligohydramnios (per exclusion criterion 6, Section 4.3). The AFI should be measured using the 4-quadrant method (see SPM for details). An abdominal ultrasound to assess fetal growth will be done at Screening (unless records are available documenting ultrasound-derived estimated fetal weight and head circumference within 3 weeks of Screening, with the results and date of assessment recorded in the eCRF).

If the investigator determines a subject suitable for retreatment (see Section 3.1.3.1 for retreatment criteria), an abdominal ultrasound to assess fetal growth should be performed unless records are available documenting ultrasound-derived estimated fetal weight and

head circumference within 3 weeks of retreatment, with the results and date of assessment recorded in the eCRF.

6.3.12.5. Laboratory Assessments

The following laboratory tests will be performed locally:

- Liver function tests, including ALT and bilirubin, performed at Screening (see Section 6.3.1)

If additional nonprotocol-specified laboratory assessments are performed at the institution's local laboratory and result in a change in subject management or are considered clinically significant by the investigator (e.g., SAE or AE or dose modification), the results must be recorded on the subject's eCRF. Refer to the SPM for appropriate processing and handling of samples to avoid duplicate and/or additional blood draws.

With the exception of the above, all protocol-required laboratory assessments, as defined in [Table 5](#), must be performed by the central laboratory. For subjects that do not deliver at the investigative center, central laboratory assessments for hematology, chemistry, and liver function tests should be performed at the investigative center within 1 week (acceptable range: 3 to 14 days) after completion of the study drug infusion.

Laboratory assessments must be conducted in accordance with the Central Laboratory Manual and protocol Time and Events Table. Laboratory requisition forms must be completed and samples must be clearly labeled with the subject number, protocol number, site/center number, and visit date. Details for the preparation and shipment of samples will be provided by the central laboratory. Reference ranges for all safety parameters will be provided to the site by the central laboratory.

The biological samples collected over the course of the study that are directly related to the conduct and analysis of the study, including hematology and chemistry tests, and liver function tests are summarized further in [Appendix 5](#).

6.3.12.6. Electrocardiogram

A single 12-lead ECG will be obtained prior to dosing (after the subject has been in a supine position for 10 to 15 minutes). If the investigator determines there is a clinically significant ECG abnormality, the subject will not be dosed and will be withdrawn from the study. Performance of a follow-up ECG after an abnormal finding will be at the discretion of the investigator.

6.3.12.7. Breastfeeding Status

A questionnaire will be administered at the maternal post-delivery assessment to assess the status of breastfeeding, as appropriate.

Details regarding the questionnaire content and administration are provided the SPM.

6.3.12.8. Maternal Depression

The effect of preterm labor, the prevention of preterm labor, and the impact of preterm birth on maternal health status will be assessed using the EPDS. The EPDS is a 10-item self-reported assessment of depression, validated for administration during both the antenatal and the post-natal periods. Items are rated on a 4-point variable Likert scale, ranging from 0 to 3. A score of 12+ indicates an increased probability of depression and investigators or designated study center personnel will be notified immediately in order to follow-up with the subject to ensure safety. Certain items in the scale also assess anxiety and will be used to assess level of anxiety. The EPDS will be administered to mothers at the maternal follow-up assessment 6 weeks (-2 weeks/+6 weeks) post-delivery ([Table 5](#)).

Additional details regarding the questionnaire administration, recording of health outcomes data, and collection and storage of the information are provided in the SPM.

6.4. Health Outcomes

- Assess maternal and neonatal health care resource use associated with preterm labor and preterm delivery. Health care resource use of interest include:
 - Maternal hospital admission (e.g., length of stay, hospital unit and type) and resource use (e.g., use of transport services, admission to extended stay facility)
 - Neonatal interventions of interest (e.g., parenteral nutrition, surfactants, blood products), procedures (e.g., imaging, such as ultrasound, computed tomography, etc.), and surgical procedures.
- Assess maternal health status (EQ-5D-5L) at time of IP administration and 6 weeks (-2 weeks/+6 weeks) after delivery

6.4.1. Health Outcomes – Maternal

6.4.1.1. Maternal Health Care Resource Use

Details on maternal health care resource use (both for hospitalizations related to preterm labor not resulting in a delivery and hospitalizations related to preterm labor/normal labor resulting in a delivery) associated with an episode of preterm labor, preterm delivery, and normal term delivery will be recorded in the eCRF. The following information will be collected in the eCRF:

- Hospital admissions for preterm labor and normal term labor: number of hospital admissions related to preterm labor/preterm delivery, length of hospital stay (in days, hours) associated with hospital admission for preterm labor and normal term labor/term delivery, and associated hospital unit and type
- Health care resource use associated with preterm labor and normal term delivery: whether the mother was transported to the hospital and by what means (ground/aircraft), whether the mother was discharged to an extended stay facility for bed rest and days spent at extended stay facility prior to delivery, whether the mother was discharged home on uterine activity monitoring and days monitored, and delivery method (vaginal, Cesarean section).

6.4.1.2. Maternal Subject-Reported Health Assessments

The effect of preterm labor, the prevention of preterm labor, and the impact of preterm birth on maternal health status will be assessed using the EQ-5D-5L self-administered questionnaire:

- The EQ-5D-5L consists of 2 pages (the EQ-5D-5L descriptive system and the EQ visual analogue scale [EQ VAS]) plus a cover page. The descriptive system comprises mobility, self-care, usual activities, pain/discomfort, anxiety/depression, with each dimension having 5 response levels: no problems, slight problems, moderate problems, severe problems, and extreme problems. The respondent is asked to indicate her health state by ticking (or placing a cross) in the box against the most appropriate statement in each of the 5 dimensions. This decision results in a 1-digit number expressing the level selected for that dimension. The digits for 5 dimensions can be combined in a 5-digit number describing the respondent's health state.

The EQ VAS records the respondent's self-rated health on a 20-cm vertical, VAS with endpoints labeled "the best health you can imagine" and "the worst health you can imagine."

This information can be used as a quantitative measure of health as judged by the individual respondents. The EQ-5D-5L will be administered to mothers early in the drug delivery phase (while the mother is still in active preterm labor) and at the maternal follow-up assessment 6 weeks (-2 weeks/+6 weeks) after delivery (Table 5).

Additional details regarding the questionnaire administration, recording of health outcomes data, and collection and storage of the information are provided in the SPM.

6.4.2. Health Outcomes – Neonatal

6.4.2.1. Neonatal Hospital Admission

For the delivery visit hospitalization, the length of the hospital stay (days) and associated hospital unit (NICU, nursery level, or level of care 1 to 4) will be recorded. In addition, whether the baby was transported to a different hospital or extended stay facility and length of stay (days) and number of hospital readmissions in the month following discharge from the delivery visit hospitalization will also be captured.

6.4.2.2. Neonatal Health Care Resource Use

Details of neonatal health care resource use associated with neonatal comorbidities of interest will be recorded in the eCRF.

In addition to capturing health care resource use associated with neonatal morbidities, the following resource use, which may or may not be associated with neonatal comorbidities of interest, should be captured:

- Use of parenteral nutrition, including number of days of use

- Use of surfactant and number of doses administered
- Imaging (ultrasound, computed tomography, magnetic resonance imaging, radionuclide)
- Other surgical procedures

6.5. Pharmacokinetics

The PK analysis will determine retosiban clearance and volume of distribution and the effect of covariates on these parameters. Plasma analysis will be performed under the control of GSK PTS-Drug Metabolism and Pharmacokinetics/Scinovo. Concentrations of retosiban will be determined in plasma samples using the currently approved bioanalytical methodology. Raw data will be archived at the bioanalytical site.

The samples collected for PK analyses are summarized further in [Appendix 5](#).

6.5.1. Sampling

Maternal blood samples for the quantification of retosiban in plasma will be taken at the following sampling windows (relative to the start of the infusion on Day 1): 2 to 4 hours, 10 to 14 hours, 22 to 26 hours, and 48 to 54 hours, the last point being after the end of the infusion. Samples may be taken at any time within these windows, but the exact time of the sample should be recorded in the eCRF.

Additionally, a maternal blood sample should be collected at the same time as the cord blood sample (see Section [6.5.2](#)) if the sample time does not already coincide with one of the PK sampling windows listed above.

A blood sample also should be taken at the onset of any maternal or fetal SAE that occurs within 12 hours after completion or discontinuation of IP.

6.5.2. Umbilical Cord Blood

For those subjects who deliver at the investigative center, a single cord blood sample will be collected and divided for biomarker assays (Section [6.8](#)) and potential genetic research (Section [6.9](#)). If subjects deliver at the investigative center within 12 hours following completion or discontinuation of IP, the cord blood sample will also be used for a PK assessment of fetal drug exposure. If the investigator deems that umbilical cord blood is needed to provide care for the infant (e.g., neonatal transfusion or laboratory testing), collection for clinical use will be prioritized over sampling for the study.

Samples from retosiban-treated subjects with concomitant use of inhibitors of BCRP or P-gp will be analyzed for drug-drug interactions. The date and time of the sample should be noted in the eCRF.

6.5.3. Retosiban Levels in Breast Milk

If breast milk/colostrum is expressed within 12 hours of receiving study treatment, a small sample (0.25 mL) will be collected and analyzed to determine if retosiban is present in the sample. The date and time of the sample should be noted in the eCRF.

- Breast milk/colostrum produced prior to 4 hours of the completion or discontinuation of the study treatment will not be permitted to be consumed but will be collected for evaluation.
- A sample of breast milk/colostrum produced between 4 and 12 hours from receiving study treatment will be collected for evaluation, and the remainder can be consumed if the potential benefits to the infant are believed to outweigh the potential risks. The subject should be advised on the potential risks associated with feeding the infant her breast milk/colostrum that was expressed within 12 hours of the completion or discontinuation of the study treatment.
- Breast milk produced more than 12 hours after the completion or discontinuation of the study treatment will not be tested and there will be no restrictions on consumption given that the time frame is beyond 5 half-lives of retosiban.

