1.3.1. Risk Assessment

Table 1 Potential Risks of Clinical Significance

Retosiban [e.g., GSK221149]		
Potential Risk of Clinical Significance	Summary of Data / Rationale for Risk	Mitigation Strategy
Fetal exposure through placental transfer	
Retosiban is a substrate of P-gp and BCRP transporters, which are thought to play a role in keeping xenobiotics out of the CNS and out of the fetal blood.
 
The preclinical data indicate very minimal, if any, maternal CNS penetration or placental transfer of retosiban as supported by:
 
 • In pregnant monkeys, there was no detectable retosiban in the cord blood when mothers were dosed up to 100 mg/kg (~7-fold human exposure). However, approximately 4% of circulating drug was detected in the cord blood when mothers were dosed at 300 mg/kg (~24-fold human exposure). • In reproductive toxicology studies in monkeys, where retosiban was given to pregnant monkeys, there were no adverse mother or infant behavioral, locomotor effects observed that were suggestive of CNS toxicity. • In rodent neurobehavioral safety studies, there were no adverse clinical signs observed at doses up to 1000 mg/kg. 
Adverse events and serious AEs reported in retosiban clinical trials to date have not indicated that retosiban has access to the maternal or fetal CNS; however, this has not been rigorously investigated.
 
The short half-life of retosiban (~2 hours) is expected to minimize any significant risk.
	
Maternal blood and cord blood samples will be analyzed for levels of retosiban in women who deliver at an investigative center within 12 hours of the completion or discontinuation of the study infusion.
 
Infants exposed to retosiban in utero will be followed for a minimum of 5 years in a separate follow-up study to assess overall safety and neurodevelopmental outcomes.
 
Unblinded safety data will be monitored by an IDMC.

Retosiban [e.g., GSK221149]		
Potential Risk of Clinical Significance	Summary of Data / Rationale for Risk	Mitigation Strategy

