Neonatal exposure via breast milk	
There were no effects on offspring growth and development in monkey reproductive toxicology studies, where systemic exposure to retosiban reached 14-fold the maximum clinical exposures. These findings suggest that exposure to retosiban during pregnancy had no adverse effect on breast milk or feeding.
 
While there are no clinical data on the degree of retosiban transfer into breast milk, the available data based on physicochemical properties suggest retosiban will be excreted into breast milk if dosed close to or during the time of milk production. Given the rapid clearance of retosiban, the risk for neonatal drug exposure via breast milk appears low but could occur in the situation where the infant is fed breast milk/colostrum produced within 12 hours of the end of the infusion. Since lactogenesis is typically delayed 30 to 48 hours postpartum in mothers going to term (and is further delayed in mothers who deliver preterm), it seems unlikely that any drug would be in the plasma postpartum to transfer into the milk.
	
Breast milk/colostrum samples will be collected for measurement of retosiban when delivery occurs and lactation has started within 12 hours of receiving study treatment infusion.
 
 When breast milk/colostrum is produced prior to 4 hours of the completion or discontinuation of the study treatment, a sample will be collected for evaluation, and consumption by the baby is not permitted. When breast milk/colostrum is produced between 4 and 12 hours of the completion or discontinuation of the study treatment, a sample will be collected for evaluation, and the remainder of the breast milk can be consumed if the potential benefits to the infant are believed to outweigh the potential risks. The subject should be advised on the potential risks associated with feeding the infant her breast milk/colostrum that was expressed within 12 hours of the completion or discontinuation of the study treatment. When breast milk is produced more than 12 hours after the completion or discontinuation of study treatment, no samples will be collected for evaluation and there will be no restrictions on consumption, given that this time frame is beyond 5 half-lives of retosiban. 
Safety monitoring for signals indicating adverse effects in infants following exposure to retosiban via breastfeeding will be performed throughout the study.
 
Unblinded safety data will be monitored by an IDMC, including infants exposed to retosiban via breastfeeding.

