5.3. Treatment Assignment

Subjects will be stratified by progesterone treatment and GA. The progesterone strata will consist of subjects on established progesterone therapy or subjects not on established progesterone therapy at Screening. The GA strata are $24^{0/7}$ to $25^{6/7}$, $26^{0/7}$ to $27^{6/7}$, $28^{0/7}$ to $30^{6/7}$, or $31^{0/7}$ to $33^{6/7}$. Subjects within each stratum will be randomly assigned in 1:1 ratio to receive either retosiban or atosiban using an interactive voice response system (IVRS)/interactive web response system (IWRS) in accordance with the randomization schedule.

Retosiban and atosiban regimens are described in [Table 3](#) and [Table 4](#). The IP will be administered by study personnel during each dosing session.

The time of dosing (i.e., start of the infusion) will be designated as time 0. All subsequent time points will be in relation to this time point. Infusion and dose administration information can be found in the SPM and Study Pharmacy Manual.

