25. A breast milk/colostrum sample is only to be collected in women who deliver and produce breast milk within 12 hours after completion or discontinuation of the IP.
26. A placental tissue sample will be collected at delivery in subjects who deliver at an investigative center.
27. A maternal blood sample for genetic research will only be collected from subjects who provide separate informed consent (see [Appendix 1](#)).
28. A cord blood sample will be collected in subjects who deliver at an investigative center, if additional consent is provided.
29. Testing for fetal fibronectin will be performed only at those institutions collecting the information as routine practice. Fetal fibronectin will not be used to determine study eligibility.
30. Cervical length measured by transvaginal ultrasound will be captured only at those institutions collecting the information as routine practice. Cervical length will not be used to determine study eligibility.

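### Section 6.5.3 times one breast-milk rule from two different starting points; the intent is clear elsewhere, and a short wording correction removes the conflict

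*Protocol*

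**What the plan says.** Section 6.5.3 has an opening sampling sentence and three bands.

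- Opening sentence: "If breast milk/colostrum is expressed within 12 hours of receiving study treatment, a small sample (0.25 mL) will be collected".
- Under 4 h: not to be consumed, but sampled. Counted from completion or discontinuation of treatment.
- 4 to 12 h: "A sample of breast milk/colostrum produced between 4 and 12 hours from receiving study treatment will be collected for evaluation"; the remainder may be fed if benefit is judged to outweigh risk. The next sentence, on advising the mother, counts its 12 h from completion or discontinuation.
- Over 12 h: counted from completion or discontinuation. No testing, and "there will be no restrictions on consumption given that the time frame is beyond 5 half-lives of retosiban".

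Section 5.3 states: "The time of dosing (i.e., start of the infusion) will be designated as time 0", and adds that later time points are measured from it.

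Elsewhere the rule runs from the end of treatment. In the breast-milk row of Table 1 (Section 1.3.1), the middle band covers milk "produced between 4 and 12 hours of the completion or discontinuation of the study treatment, a sample will be collected for evaluation", and the other two bands use the same origin. Table 5 note 25 restricts sampling to women who deliver and "produce breast milk within 12 hours after completion or discontinuation of the IP". Sections 3.1 and 3.1.4 agree. Appendix 5 uses the same origin, although its 12 h attaches to delivery. The one other loose wording is the lead sentence of that Table 1 row, which requires that "lactation has started within 12 hours of receiving study treatment infusion".

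**The concern.** Three consecutive time bands cover the period after treatment without overlap or gap only if they share an origin. Here the first and third bands run from the end of the infusion, while the second, with the sampling trigger, is worded from receipt of treatment. The infusion lasts up to 48 h, so the choice of origin can move a band by up to 48 h. Because Section 5.3 fixes time 0 at the start of the infusion, a site working from Section 6.5.3 alone has some textual ground for the start-time reading. At stake are an instruction on what a newborn may be fed and the completeness of the milk samples.

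A second, lesser question concerns the reason given for lifting restrictions at 12 h. It rests on a half-life stated without reference to CYP3A4 inhibition, yet strong inhibitors that cannot be stopped are permitted (Section 5.8.1.5).

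**Working it through.** **The two clocks.** Let L be the hours from start to end of infusion, and t the hours from start of infusion to milk production.

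- First band: t − L < 4.
- Third band: t − L > 12.
- Second band, end-of-treatment reading: 4 ≤ t − L ≤ 12. The three bands then cover all times after treatment, each once.
- Second band, start-of-infusion reading: 4 ≤ t ≤ 12.

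On the start-of-infusion reading:

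1. *Early stop.* The first and second bands overlap whenever the infusion ends before 12 h. With L = 10 and t = 11, the time since the end is 11 − 10 = 1 h, so the first band bars the milk. The time since the start is 11 h, so the second band allows it conditionally.
2. *Full infusion.* With L = 48, the second band closes 48 − 12 = 36 h before the infusion ends. The first band ends at 48 + 4 = 52 h and the third begins at 48 + 12 = 60 h. Taken literally, no band covers 52 to 60 h.
3. *Sampling trigger.* It would close at 12 h from the start, against 48 + 12 = 60 h under Table 5 note 25.

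The 52 to 60 h interval is 4 to 12 h after the end of treatment. Table 1's middle band covers it, and the advice sentence within the second band of 6.5.3 reaches it.

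**The half-life basis.** Table 1 gives the input: "The short half-life of retosiban (~2 hours) is expected to minimize any significant risk".

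- Plan's figure: 12 / 2 = 6 half-lives, with 0.5^6 = 1.6% left. The statement that 12 h exceeds five half-lives is reproduced.
- Limit: 12 / 5 = 2.4 h, that is, 2.4 / 2 = 1.2 times the stated value.

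The documents give no half-life under a strong CYP3A4 inhibitor. The following are assumptions, shown only to indicate the range.

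- Section 5.1.1.1 gives 2 mg/h in place of 6 mg/h for comparable exposure. If this reflects clearance at 2/6 = 1/3 and volume is unchanged, the half-life is 2 × 3 = 6 h. Then 12 h is 2 half-lives (25% left), and five half-lives take 30 h.
- Ratio of the ketoconazole effects on AUC and Cmax in Table 1: 2 × 8.7 / 5.2 = 3.35 h. Then 12 h is 3.6 half-lives (8.3% left), and five take 16.7 h.
- The whole 8.7-fold AUC rise taken as systemic clearance: 2 × 8.7 = 17.4 h. Then 12 h is 0.7 half-lives (62% left), and five take 87 h. The rise was measured with oral dosing, so this is an upper bound.

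Auto-induction, also noted in Table 1, works the other way. In the 6-h case it would have to shorten the half-life 6 / 2.4 = 2.5-fold for 12 h to suffice. The simulated concentrations in Section 3.2.1.1 fall between 2 h and 48 h by 388 / 128 = 3.0 at the upper ends and 50 / 8.9 = 5.6 at the lower ends. Those range ends are not paired, no cause is named, and inhibition is not modelled.

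**The case against.** The strongest reply is that this is an editorial slip the protocol already resolves. The advice sentence in the same bullet counts from the end of treatment. Section 3.1.4 does too, and so does Table 5, whose requirements Section 3.1 makes mandatory. The start-of-infusion reading is implausible for a completed infusion, because it puts the whole 4 to 12 h band during dosing. When the pharmacokinetic sections do mean the start of the infusion, Section 6.5.1 says so. In the early-stop example the first band is a flat prohibition, which a careful site would follow.

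All of this stands, and it fixes the size of the point. It does not make the wording consistent: the two origins remain in one rule, and one of them has some support from Section 5.3.

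A reader might go further and infer a real hole in protection at 52 to 60 h after a full infusion. The documents do not support that. The interval is empty only if the second band is read from the start and its own advice sentence, Table 1 and Table 5 note 25 are all set aside.

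**Conclusion.** Section 6.5.3 is inconsistent as written and should be corrected. The mixed wording is visible on the page and needs no assumption. The conflicting instruction follows only if receipt of treatment is taken as the start of the infusion, and only for infusions stopped before 12 h. The intent is clear elsewhere, so the point is minor. Milk concentrations are only listed (SAP Sections 8.3 and 9), so no endpoint, test or estimate depends on it.

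The half-life question is a secondary note and not a demonstrated error. It would be tempting to conclude that the 12-h limit is wrong, or unsafe, for women on a strong inhibitor. The documents do not show this: the inhibited half-life is inferred from a dosing rule or from oral data, the inferred values run from 3.35 to 17.4 h, and auto-induction could offset them by an unknown amount. What can be said is that the stated basis is not established for these women. Few are likely to be affected, and Table 1 also relies on late lactogenesis (30 to 48 h postpartum), animal offspring data and review by the data monitoring committee.

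**What to change.** In the opening sentence and the 4 to 12 h bullet of Section 6.5.3, replace *receiving study treatment* with *completion or discontinuation of the study treatment*. Make the same replacement for *receiving study treatment infusion* in the lead sentence of the Table 1 breast-milk row. This is wording only: it adds no sample, visit or restriction, and it brings the text into line with Table 5 note 25 and Section 3.1.4.

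Separately, ask the sponsor to confirm from its own pharmacokinetic data whether 12 h is adequate for women on the strong-inhibitor regimen. No longer window is proposed, because the documents cannot set one. Any extension would have a cost to weigh: under the blinding in Section 5.4 it would also apply to infants in the atosiban arm, who have no retosiban exposure.
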